5.3 LIFESTYLE CONSIDERATIONS

5.3.1 Meals and dietary restrictions

1. Refrain from consumption of grapefruit or grapefruit containing products, or Seville oranges from 7 days before the start of study intervention until after the final dose.
2. Fasting (except water) 1 hour prior to and 1 hour after each SAR442720 dose is required. On days when both medications are administered together, fasting is requisite due to the requirements of SAR442720. For participants in Part-3, adagrasib may be taken with or without food. When co-administered with SAR442720, adagrasib should be taken without food (as SAR442720 requirement). For participants enrolled in Part-4, meal consumptions will be based on the protocol instructions. Vegan and non-vegan meals are defined in the protocol and are comparable in terms of kilocalories as well as fat consumption and similar to classic meals in terms of fed conditions (non-vegan meals will be provided except for patients who are vegans). Please see Appendix 13 ([Section 10.13](#)).

5.4 SCREEN FAILURES

Screen failures are defined as participants who consent to participate in the clinical study but are not subsequently able to receive treatment in the study. A minimal set of screen failure information is required to ensure transparent reporting of screen failure participants to meet the Consolidated Standards of Reporting Trials (CONSORT) publishing requirements and to respond to queries from regulatory authorities. Minimal information includes demography, screen failure reasons, eligibility criteria, and any SAE.

Individuals who do not meet the criteria for participation in this study (ie, screen failure) may be rescreened without a new ICF if within 5 days of the initial screening date of screen failure. Rescreened participants should be assigned the same participant number as for the initial screening, if within 5 days of initial screening. Only hematology, chemistry, and coagulation tests may need to be repeated if outside the screening window. Other clinical testing will not need to be repeated if outside screening window (ie, within 5 days).

6 STUDY INTERVENTION

Study intervention is defined as any investigational intervention(s), marketed product(s), placebo, or medical device(s) intended to be administered to a study participant according to the study protocol.

6.1 STUDY INTERVENTION(S) ADMINISTERED

Table 16 - Overview of study interventions administered in Part-1, -2, and -4

Study Intervention name	SAR442720		Pembrolizumab
Type	Drug		
Dose formulation	Powder-in-capsule	Film-coated tablet	Lyophilized powder in single-dose vial for reconstitution or solution in a single-dose vial
Unit dose strengths	20 mg and 100 mg		50 mg/vial or 100 mg/4 mL (25 mg/mL)
Dosage levels	The starting dose depends on which combination is evaluated		200 mg Q3W or 400 mg Q6W (for Part-2)
Route of administration	Oral with water after 1 hour fast; no food or drink (other than water) allowed for 1 hour after administration		Intravenous infusion over 30 minutes in accordance with the product leaflet
Use	Experimental combination		
IMP and NIMP	IMP		
Packaging and labeling	SAR442720 capsule will be provided in 8-count HDPE bottles	SAR442720 tablets will be provided in a wallet containing 1 Aclar blister of 8 tablets	Pembrolizumab will be provided in 50 mg lyophilized powder in single-dose vial for reconstitution or 100 mg/4 mL (25 mg/mL) solution in a single-dose vial
	Each bottle will be labeled as required per country requirement	Each wallet will be labeled as required per country requirements	Each box will be labeled as required per country requirement
Current/Former names or aliases	SAR442720, RMC-4630, RMC 0694630	SAR442720	KEYTRUDA®, pembrolizumab

Abbreviation: BID = twice daily; BIW = Day 1 and Day 2 of each week, Day 1 and Day 4 of each week, or any other emergent dose schedule from the ongoing Phase 1 monotherapy escalation study; HDPE, high-density polyethylene, IMP, investigational medical product; NIMP, noninvestigational medical product; Q3W = once every 3 weeks; Q6W, Q3W = once every 3 weeks.

Table 17 - Overview of study interventions administered in Part-3

Study Intervention name	SAR442720	Adagrasib
Type	Drugs	
Dose formulation	Powder-in-capsule	Film coated tablets
Unit dose strengths	20 mg and 100 mg	200 mg
Dosage levels	The starting dose depends on which combination is evaluated	400 mg BID or 600 mg BID; should be at 12-hour intervals to the extent possible
Route of administration	Oral with water after 1 hour fast; no food or drink (other than water) allowed for 1 hour after administration	Oral with at least 240 mL (8 ounces) of water; may be taken with or without food
Use	Experimental combination	
IMP and NIMP		IMP
Packaging and labeling	SAR442720 capsule will be provided in 8-count HDPE bottles Each bottle will be labeled as required per country requirements	Adagrasib tablets will be provided in 132-count HDPE bottles Each bottle will be labeled as required per country requirements
Current/Former names or aliases	SAR442720, RMC-4630, RMC 0694630	MRTX849, adagrasib

Abbreviation: BID = twice daily; HDPE, high-density polyethylene, IMP, investigational medical product; NIMP, noninvestigational medical product.

6.1.1 Investigational medicinal product

The number of SAR442720 20 mg and 100 mg bottles and adagrasib 200 mg bottles will be dispensed depending on the dose level and will cover the treatment until the next dispensation visit.

When applicable, pembrolizumab will be sourced from available commercial supplies. Otherwise it will be relabeled by the Sponsor as per country requirements and according to Good Manufacturing Practice (GMP) guidelines.

Further details on IMPs will be described in the Pharmacy Manual.

Between the protocol-scheduled on-site visits, interim visits may be required for IMP dispensing. As an alternative to these visits, SAR442720 20 mg and 100 mg bottles and adagrasib 200 mg bottles may be supplied from the site to the participant via a Sponsor-approved courier company where allowed by local regulations and approved by the participant (Direct-To-Patient [DTP] process).

6.1.2 Non-investigational medicinal product

Appropriate premedication for study treatments may be administered at the Investigator's discretion according to the usual clinical practice and in accordance with institutional guidelines. If premedication is required, all the drugs used will also be entered to the concomitant medication pages.

6.2 PREPARATION/HANDLING/STORAGE/ACCOUNTABILITY

SAR442720 (powder-in-capsule drug products: 20 mg and 100 mg) is stored as following: Store below 30°C (86°F). Do not freeze.

SAR442720 (aclar/aluminum blister tablets: 20 mg and 100 mg) is stored as follows: Store between 2°C and 30°C (36°F to 86°F). Do not freeze.

Pembrolizumab is stored as follows:

- Lyophilized powder: Store vials under refrigeration at 2°C to 8°C (36°F to 46°F).
- Solution: Store vials under refrigeration at 2°C to 8°C (36°F to 46°F) in original carton to protect from light. Do not freeze. Do not shake.

Adagrasib is stored as follows:

- MRTX849 tablets are provided in single bottles (no cartons) and should be stored at room temperature (2°C to 25°C, 36°F to 77°F) according to the instructions on the label.
- The Investigator or designee must confirm appropriate temperature conditions have been maintained during transit for all study intervention received and any discrepancies are reported and resolved before use of the study intervention.
- Only participants enrolled in the study may receive study intervention and only authorized site staff may supply or administer study intervention. All study intervention must be stored in a secure, environmentally controlled, and monitored (manual or automated) area in accordance with the labeled storage conditions with access limited to the Investigator and authorized site staff.
- The Investigator, institution, or the head of the medical institution (where applicable) is responsible for study intervention accountability, reconciliation, and record maintenance (ie, receipt, reconciliation, and final disposition records).

Any quality issue noticed with the receipt or use of an IMP (deficiency in condition, appearance, pertaining documentation, labeling, expiration date, etc) must be promptly notified to the Sponsor. Some deficiencies may be recorded through a complaint procedure (see [Section 8.3.7](#)).

A potential defect in the quality of IMP may be subject to initiation of a recall procedure by the Sponsor. In this case, the Investigator will be responsible for promptly addressing any request made by the Sponsor, in order to recall the IMP and eliminate potential hazards.

Under no circumstances will the Investigator supply IMP to a third party (except for DTP shipment, for which a courier company has been approved by the Sponsor), allow the IMP to be used other than as directed by this clinical trial protocol, or dispose of IMP in any other manner.

6.3 MEASURES TO MINIMIZE BIAS: RANDOMIZATION AND BLINDING

This is an open label study without randomization. No blinding or randomization will be used for this study. In order to minimize bias, the participants will be assigned sequentially as they are enrolled into the study using the inclusion and exclusion criteria as outlined in [Section 5.1](#) and [Section 5.2](#). Enrollment will be confirmed by the sponsor Medical Monitor after review of all supporting documentation for eligibility criteria.

Participants will be allocated a screening number at the time of signing the ICF. If a participant is a screen failure, the number will not be reassigned.

6.4 STUDY INTERVENTION COMPLIANCE

When participants are dosed at the site, they will receive study intervention directly from the Investigator or designee, under medical supervision. The date and time of each dose administered in the clinic will be recorded in the source documents and recorded in the case report form (CRF). The dose of study intervention and study participant identification will be confirmed at the time of dosing by a member of the study site staff other than the person administering the study intervention.

When participants self-administer study intervention(s) at home, compliance with study intervention will be assessed at each visit. Compliance will be assessed by direct questioning, counting returned capsules and checking the participant diary information during the site visits and documented in the source documents and CRF. Deviation(s) from the prescribed dosage regimen should be recorded in the eCRF.

A record of the number of SAR442720 capsules, SAR442720 tablets, and adagrasib tablets dispensed to and taken by each participant must be maintained and reconciled with study intervention and compliance records. Intervention start and stop dates, including dates for intervention delays and/or dose reductions will also be collected and recorded in eCRF.

6.4.1 Missed dose

SAR442720: If a participant misses a dose, it may be taken at the time the omission was discovered as long as it is within 24 hours of the original administration time. Otherwise, the dose should not be administered and should be recorded as an omission. The participant should not administer more than the recommended dose.

Adagrasib: If a dose is inadvertently missed, the dose should be skipped if >4 hours has elapsed since the expected dosing time. Dosing may resume at the next schedule time.

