 - Participants who discontinue study treatment with radiological or clinical progressive disease (PD) (per [Response Evaluation Criteria in Solid Tumors (RECIST)] v1.1) or iCPD (per iRECIST) will be followed in the Follow-Up Visit 1 occurring 3 months \pm 5 days from last IMP administration, or until start of new anticancer therapy or cohort cut-off, whichever comes first, before moving to the Survival Phone Call Follow-Up Period.

For Part-2 and Part-3B, the primary endpoint (objective response rate [ORR]) analyses is performed when all participants have at least 2 post baseline tumor assessments with response durability demonstrated or discontinue study treatment (whichever occurs first).

Study intervention(s)

Investigational medicinal products

SAR442720 capsules

- Formulation: SAR442720 capsules are supplied as powder-in-capsule drug products of 20 mg and 100 mg. The capsules are packaged in high-density polyethylene (HDPE) bottles.
- Route of administration: Oral with water after 1 hour fast; no food or drink (other than water) allowed for 1 hour after administration (C1D1, C1D15 and C2D1 in Part-4 are exceptions).
- Dose regimen: SAR442720 capsules will be administered orally BIW (Day 1 and Day 2 of each week or, Day 1 and Day 4 of each week, or any other emergent dose schedule from the ongoing Phase 1 monotherapy escalation study). The starting dose is 140 mg on Day 1 and Day 4 each week in Part-1 and 100 mg BIW, Day 1 and Day 2 in Part-3A. The dosing regimen of Part-2 and Part-4 is 200 mg on Day 1 and Day 2 BIW.

SAR442720 tablets

- Formulation: SAR442720 tablets are supplied as film-coated tablets drug products of 20 mg and 100 mg. The tablets are packaged in Aclar blisters containing 8 tablets.
- Route of administration: Oral with water after 1 hour fast; no food or drink (other than water) is allowed for 1 hour after administration (C1D1, C1D15, and C2D1 in Part-4 are exceptions).
- Dose regimen: SAR442720 tablets will be administered orally BIW (Day 1 and Day 2 of each week or, Day 1 and Day 4 of each week, or any other emergent dose schedule from the ongoing Phase 1 monotherapy escalation study). The dosing regimen of Part-4 is 200 mg on Day 1 and Day 2 BIW.

Pembrolizumab

- Formulation: 50 mg lyophilized powder in single-dose vial for reconstitution or 100 mg/4 mL (25 mg/mL) solution in a single-dose vial
- Route of administration: IV infusion

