Day 8 ^d	Predose	Within 1 hour before Day 8 dose			
Day 15	Predose	Within 1 hour before Day 15 dose			
Cycle 2					
Day 1	Predose ^c	Within 1 hour before Day 1 dose	Day 1	Predose ^c	Within 1 hour before Day 1 dose
	2 hours	±10 minutes			
	8 hours ^e	±30 minutes			
Day 2 ^d	2 hours ^e	±10 minutes			
Cycle 6					
Day 1	Predose ^c	Within 1 hour before Day 1 dose	Day 1	Predose ^c	Within 1 hour before Day 1 dose
EOT	X	Any time during visit			

Abbreviations: EOT = end of treatment; PK = pharmacokinetic(s).

a PK samples = one 1.5 mL sample required per time point.

b Windows are relative to the nominal time point.

c PK samples for SAR442720 and pembrolizumab will be collected at the same time points.

d Only for Day 1, Day 2 of each weekly dosing schedule

e Only collected during Part-1.

Table 6 - PK time points (Part-3A dose escalation)

SAR442720		Adagrasib	
Study Day	PK Time points ^a	Window ^b	PK Time points ^a
Cycle 1			
Day 1	Predose	Within 1 hour before Day 1 dose	Predose
	0.5 hour ^c	±10 minutes	1 hour
	1 hour	±10 minutes	2 hours
	2 hours	±10 minutes	4 hours
	4 hours	±10 minutes	6 hours
	6 hours	±30 minutes	8 hours ^d
Day 2	12 hours ^d		Within 1 hour before D1 evening dose
	24 hours after D1 dose	Within 1 hour before Day 2 dose	12 hours after D1 evening dose
Day 8	Predose	Within 1 hour before Day 8 dose	Predose
Day 15	Predose	Within 1 hour before Day 15 dose	Predose
	0.5 hour ^c	±10 minutes	1 hour
	1 hour	±10 minutes	2 hours
	2 hours	±10 minutes	4 hours
	4 hours	±10 minutes	6 hours
	6 hours	±30 minutes	8 hours ^d
Day 16	24 hours after D15 dose	Within 1 hour before Day 16 dose	12 hours after D15 evening dose
	2 hours ^c	±10 minutes	-
Cycle 2, 3 and Cycle 4			
Day 1	Predose	Within 1 hour before Day 1 dose	Predose
EOT	X	Any time during visit	X
Abbreviations: EOT = end of treatment, PK = pharmacokinetic(s).			

a For samples where both SAR442720 and adagrasib are collected, they could be collected at the same time points.

b Windows are relative to the nominal time point.

c SAR442720 only PK samples.

d Adagrasib only PK sample, 12-hour sample on Day 1 is optional to collect.

Table 7 - PK time points (Part-3B Dose Expansion)

SAR442720			Adagrasib	
Study Day	PK Time points^a	Window^b	PK Time points^a	Window^b
Cycle 1				
Day 1	Predose	Within 1 hour before Day 1 dose	Predose	Within 1 hour before Day 1 morning dose
	2 hours ^c	±10 minutes	-	-
	6 hours	±30 minutes	6 hours	±30 minutes

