Day 8	Predose	Within 1 hour before Day 8 dose	Predose	Within 1 hour before Day 8 morning dose
	Predose	Within 1 hour before Day 15 dose	Predose	Within 1 hour before Day 15 morning dose
	2 hours ^c	±10 minutes	-	-
Day 15	6 hours	±30 minutes	6 hours	±30 minutes
Cycle 2, 3 and 4				
Day 1	Predose	Within 1 hour before Day 1 dose	Predose	Within 1 hour before Day 1 dose
EOT	X	Any time during visit	X	Any time during visit

Abbreviations: EOT = end of treatment, PK = pharmacokinetic(s).

a For samples collected for both SAR442720 and adagrasib can be collected at the same time points.

b Windows are relative to the nominal time point.

c SAR442720 only PK samples.

Table 8 - PK time points for Part-4

SAR442720			Pembrolizumab		
Study Day	PK Time points ^a	Window ^b	Study Day	PK Time points ^a	Window ^b
Cycle 1					
Day 1	Predose ^c	Within 1 hour before Day 1 dose	Day 1	Predose ^c	Within 1 hour before Day 1 dose
	0.5 hour	±5 minutes			
	1 hour	±10 minutes			
	2 hours	±10 minutes			
	4 hours	±30 minutes			
	8 hours	±30 minutes			
Day 2	24 hours post Day 1 dose	Within 1 hour before Day 2 dose	-	-	-
Day 8	Predose	Within 1 hour before Day 8 dose	-	-	-
Day 15	Predose ^c	Within 1 hour before Day 1 dose	-	-	-
	0.5 hour	±5 minutes			
	1 hour	±10 minutes			
	2 hours	±10 minutes			
	4 hours	±30 minutes			
	8 hours	±30 minutes			
Day 16	24 hours post Day 15 dose	Within 1 hour before Day 16 dose	-	-	-
Cycle 2					
Day 1	Predose ^c	Within 1 hour before Day 1 dose	Day 1	Predose ^c	Within 1 hour before Day 1 dose
	0.5 hour	±5 minutes			
	1 hour	±10 minutes			
	2 hours	±10 minutes			
	4 hours	±30 minutes			
	8 hours	±30 minutes			
Day 2	24 hours post Day 1 dose	Within 1 hour before Day 2 dose	-	-	-
Cycle 6					
Day 1	Predose ^c	Within 1 hour before Day 1 dose	Day 1	Predose ^c	Within 1 hour before Day 1 dose
EOT	X	Any time during visit	-	-	-

Abbreviations: EOT = end of treatment; PK = pharmacokinetic(s).

a PK samples = one 1.5 mL sample is required per time point.

b Windows are relative to the nominal time point.

c PK samples for SAR442720 and pembrolizumab will be collected at the same time points.

Table 9 - Pharmacodynamic/biomarker sampling time points (Part-1 and Part-2)

Study Day	RNA Biomarker Time points ^a	Blood germline testings ^b	ctDNA Biomarker Time points ^c	Immune cell profiling time points ^d	Cytokines time points ^e	Window ^f
Cycle 1						
Day 1	Predose	Predose	Predose	Predose	Predose	Within 1 hour before Day 1 dose
Day 15	Trough		Trough	Trough	Trough	

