Part-2 of the study will start once RP2D for SAR442720 from Part-1 is confirmed. The SAR442720 RP2D will be 200 mg BIW, Day 1 and Day 2 of each week, administered orally (21 days per cycle). This dose emerged as the safe dose of SAR442720 from the escalation part (Part-1) of this study. Pembrolizumab will be administered as a dose of 200 mg using a 30 minutes IV infusion on Day 1 every 3 weeks (21 days cycle) or a dose of 400 mg using a 30 minutes IV infusion on Day 1 every 6 weeks (42 days cycle).

The duration of the study for a participant will include:

- Screening period: up to 28 days.
- Treatment Period: enrolled participants will receive continuous treatment until PD, unacceptable AE, other full permanent discontinuation criteria as described in [Section 7.1](#).
- End of Treatment and Follow-up: EOT visit will occur 30 days ± 5 days from last IMP administration or prior to initiation of further therapy. Participants will then enter the Observation period and will be followed differently depending on the reason leading to EOT:

- Participants who discontinue study treatment with radiological or clinical PD (per RECIST v1.1) or iCPD (per iRECIST) will be followed in the Follow-Up Visit 1 occurring 3 months \pm 5 days from last IMP administration, or until start of new anticancer therapy or cohort cut-off, whichever comes first, before moving to the Survival Phone Call Follow-Up Period.

Part-3

Part-3 of this open-label, multi-center, un-controlled, non-randomized study, will assess the safety, RP2D, anti-tumor activity, and PK of SAR442720 in combination with adagrasib in participants with NSCLC harboring KRAS G12C mutation.

Part-3A

SAR442720 and adagrasib will be administered orally on a continuous basis. The starting dose (DL1) of SAR442720 will be 100 mg on Day 1 and Day 2 BIW with adagrasib given at 400 mg BID orally. The dose escalation will follow the mTPI2 design with a minimum of 3 participants evaluable for DLT for each dose level. Participants will be DLT-evaluable if they have taken at least 80% of the scheduled Cycle 1 dose of both drugs in the first 21 days of treatment. The same mTPI-2 design as that used in Part-1 will be used in Part-3A.

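### The 24 h window for a missed SAR442720 dose equals the whole Day 1 to Day 2 interval in Parts 2 to 4, so the rule permits two full doses a few hours apart, mainly at the Day 8/Day 9 pair from Cycle 2

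*Protocol*

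**What the plan says.** Protocol Section 6.4.1 states of a missed SAR442720 dose that "it may be taken at the time the omission was discovered as long as it is within 24 hours of the original administration time". After that it is skipped and recorded as an omission. The SAR442720 paragraph ends: "The participant should not administer more than the recommended dose". It gives no minimum time to the next dose and no instruction to move or skip that dose. For adagrasib, the same section requires skipping once more than 4 h have passed.

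The consecutive-day schedule applies in three parts of the study:

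- **Part 2** (Section 4.1): "The SAR442720 RP2D will be 200 mg BIW, Day 1 and Day 2 of each week".
- **Part 3A** (Section 4.1): the starting dose "will be 100 mg on Day 1 and Day 2 BIW with adagrasib given at 400 mg BID orally". Every level in Table 14 is on D1 and D2, and Part 3B uses the dose chosen in Part 3A.
- **Part 4** (Section 1.1): "The dosing regimen of Part-2 and Part-4 is 200 mg on Day 1 and Day 2 BIW".

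The PK tables fix the planned interval. Table 6 ("24 hours after D1 dose") and Table 8 ("24 hours post Day 1 dose") each place that sample in the hour before the Day 2 dose. Tables 2, 3 and 4 allow SAR442720 to be taken at home.

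**The concern.** A missed-dose window normally leaves a safe margin before the next dose. Here the window is as long as the interval it sits in. The person deciding may be a participant alone at home, and compliance is reviewed only at the next visit (Section 6.4).

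At stake is an avoidable, protocol-compliant peak in exposure to an investigational drug. This matters most in Part 3. Section 2.3.1.5 expects adagrasib to raise SAR442720 exposure by up to 2-fold, and the starting dose was halved to 100 mg. Exposure is therefore something the sponsor already manages.

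There is also a possible clash within the protocol. Section 8.3.6 treats SAR442720 as overdosed at twice or more the intended dose within the intended therapeutic interval, which it does not give in hours, and makes a symptomatic overdose an event of special interest. Two full doses a few hours apart could arguably qualify although Section 6.4.1 was followed.

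**Working it through.** The 24 h window is an instruction, not a derived figure, so there is nothing to reproduce. The check compares it with the dosing interval. Below, first dose means the first of each weekly pair (cycle Days 1, 8 and 15).

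**1. Window as a share of the interval**
- SAR442720 on Day 1/Day 2: 24/24 = 100%.
- Adagrasib, twice daily at about 12 h: 4/12 = 33%.

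**2. Gap to an on-time next dose = interval − lateness**

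| First dose late by | Day 1/Day 2 (24 h) | Day 1/Day 4 (72 h) |
|---|---|---|
| 12 h | 12 h | 60 h |
| 15 h | 9 h | 57 h |
| 20 h | 4 h | 52 h |
| 22 h | 2 h | 50 h |
| 24 h | 0 h | 48 h |

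Half of the permitted window, (24 − 12)/24 = 0.50, leaves less than 12 h. A late second dose is harmless in this respect: the next dose is 144 h away, so at least 144 − 24 = 120 h remain.

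**3. When this can arise (clock times assumed; the documents do not fix the hour of home doses)**
- Due 08:00: found at 20:00 leaves 12 h, at 23:00 leaves 9 h, at 06:00 next day leaves 2 h.
- Due 20:00: found at 16:00 next day is 20 h late and leaves 4 h.

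Short gaps thus need discovery at night or early morning under morning dosing, but can arise in normal daytime under evening dosing.

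**4. How many pairs are open**
- Each 21-day cycle has 3 pairs.
- Cycle 1: Days 1, 8 and 15 are visits, with pre-dose PK sampling (for Day 8, "Within 1 hour before Day 8 dose").
- Cycle 2 onward: Tables 2, 3 and 4 schedule vital signs on Days 1 and 15, to be taken before dosing. That covers 2 of 3 pairs and leaves Day 8/Day 9, 1 of 3.
- Protection on Days 1 and 15 is partial: the visit windows are ±2 days, and Day 15 laboratory tests may be remote.

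Planned participants on this schedule: 40 (Part 2) + 15 to 30 (Part 3A) + 40 (Part 3B) + up to 12 (Part 4) = 107 to 122 with Part 4 full. How many doses are taken at home or late is not given.

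**5. Possible size of the peak (assumption only)**
No half-life is given. Assume instant absorption, simple superposition of the two doses, and a half-life t between 6 and 48 h. The peak after the second dose, relative to a 24 h gap, is (1 + 2^(−g/t)) / (1 + 2^(−24/t)) for a gap of g hours.

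| Assumed half-life | 4 h gap | 12 h gap |
|---|---|---|
| 6 h | +53% | +18% |
| 12 h | +43% | +20% |
| 24 h | +26% | +14% |
| 48 h | +14% | +8% |

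This shows direction and rough range. It is not an estimate for SAR442720.

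**The case against.** The strongest reply is that Section 6.4.1 already forbids this through its closing sentence, especially when read with Section 8.3.6. Part of that stands: the sentence plausibly bars taking both doses together. But it caps an amount and names no period, and two separate doses each equal the recommended dose. Section 8.3.6 is a reporting definition, not a spacing rule. A site could postpone the second dose, but nothing asks it to.

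The second reply is that the opportunity is small and the harm unknown. This largely stands. Most first doses fall on visit days. In Part 3 the evening adagrasib dose is a natural moment to notice a missed morning dose, leaving about 12 h. The weekly total is unchanged. Section 8.4 asks for monitoring until the drug is undetectable, at least 5 days, which hints at slow clearance and hence a smaller peak effect. The Pharmacy Manual and the diary, which may give spacing advice, were not available.

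Three stronger readings are tempting but unsupported:

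- A reader might infer that every weekly pair in every cycle is exposed. The visit schedules contradict this.
- A reader might infer biased DLT decisions or response rates. Cycle 1 first doses fall on visit days, and nothing in the documents links dose spacing to an endpoint.
- A reader might infer that the window was carried over by mistake from Day 1/Day 4. The amendment history fits this: amendment 02 introduced an alternative twice-weekly schedule and lists no change to 6.4.1, and amendment 04 lists only adagrasib instructions there. It does not prove it.

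**Conclusion.** The point holds as a cheap safety improvement. A stated rule, followed as written, permits two full SAR442720 doses a few hours apart on the Day 1/Day 2 schedule: 4 h apart if the first is 20 h late, against never less than 48 h on Day 1/Day 4. It might also place a compliant participant within the overdose definition.

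The size is limited mainly to one pair in three from Cycle 2 onward, among about 107 to 122 planned participants. The conclusion rests on the second dose being taken on time and on no gap being set in the Pharmacy Manual or diary. Frequency and clinical effect cannot be derived from the documents.

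**What to change.** Add one or two sentences to Section 6.4.1. For Day 1/Day 2 dosing, a late first dose may be taken only up to a cut-off shorter than 24 h, set by the sponsor from its PK data; otherwise it is skipped and recorded as an omission. A cut-off of c hours guarantees a gap of 24 − c: 12 h keeps at least 12 h, and 8 h (one third of the interval, the proportion used for adagrasib) keeps at least 16 h. The documents do not single out either value; 12 h is an example.

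Keep 24 h for a late second dose and for Day 1/Day 4. Use the same wording in the participant diary and the Pharmacy Manual; if the Manual already sets a gap, bring it into 6.4.1.

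No extra visits, samples or participants are needed. The downside is a few more omitted first doses, mostly at Day 8 of later cycles.
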